6. SPECIFIC AIMS

The purpose of this investigational device study is to collect data to support regulatory submissions, primarily in the United States of America, but it may also be used to support submissions in other regions.

The aim of this study is to better evaluate the efficacy of non-invasive electrical vestibular nerve stimulation (VeNS), together with a lifestyle modification program, as a method of reducing excess body weight, as compared to a sham control and lifestyle modification program.

Primary Objective: Establish the clinical performance of the Vestal device in patients who are overweight.

Secondary Objective: To evaluate the safety of the Vestal device relative to control group, in terms of the occurrence of adverse events, changes from baseline in vital signs (blood pressure and heart rate), and laboratory results in patients who are overweight.

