- Dietary Counseling from research dietitian including review of diet reports from Healthwatch 360 app – 15 minutes

Summary of Final Site Visit 4 (Final Site Visit) (12 months)

- Urine pregnancy test (if applicable – i.e. a female of child bearing potential)
- Weight and BMI calculation
- Check skin behind ears (visual inspection to ensure appears healthy)
- Waist and hip measurements
- Fasting Insulin level
- High Sensitivity C-Reactive Protein
- Lipid Panel
- Oral Glucose Tolerance Test (OGTT)
- Pulse rate and blood pressure
- Quality of life survey (Duke University IWQOL – <http://www.qualityoflifeconsulting.com/iwqol-lite.html>)
- DXA Scan (whole body scan)
- Coordinator asks participant to complete adverse event monitoring questionnaire.
- Audiogram test including otoscope examination of the ear canals.

Other activities at Visit 4 (12 months):

- The study participant will return the investigational device.

Frequency of Follow-Up Appointments

Visits in person at: enrollment (0 months); 3 months; 6 months; and 1 year. Telephone follow up at: weeks 2; months 1 & 9; and as required on an ad hoc basis. There will also be the facility to bring subjects in for review should concerns be raised after the telephone review – e.g. concern re skin irritation behind the ear. Study participants are also free to contact (call or email) study personnel at any time with any issues or inquiries.

Primary Outcome Measures (At 12 months)

- The difference in mean weight loss between the active-product and placebo-treated groups is at least 5% total body weight lost (TBWL), and the difference is statistically significant.
- The proportion of participants who lose 5% or more of baseline body weight in the active-product group is at least 35% and is approximately double the proportion in the placebo-treated group; the difference between groups is statistically significant.

Secondary Outcome Measures (At 12 months)

- The difference in mean percent loss of baseline total body fat in the active versus placebo treated groups. (As measured by means of a whole body DXA scan– see Appendix 4).
- The proportion of subjects who lose at least 5% of baseline total body fat in the active versus placebo treated groups. (As measured by a whole body DXA scan).
- The difference in mean percent loss of baseline truncal body fat in the active versus placebo treated groups. (As measured by a whole body DXA scan).

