Methods: Primary Aims

For total body weight loss (TBWL) as a continuous measure, we will use a two-sample t-test to examine the differences between the control and active treatment groups at each time period. We will also build one-sided confidence intervals to test whether the difference between groups exceeds a superiority margin of 5%. As a secondary analysis, we will also use a linear regression with TBWL as the dependent variable and group and other covariates of interest (gender, age, etc.) as independent variables. To assess any longitudinal effects, we will use a linear mixed effects model for weight over time, with fixed covariates for baseline weight, time, group, and a time / group interaction, and a random intercept to account for within-subject correlation. We will use a one-sided exact binomial test to determine if the response rate in the treatment group significantly exceeds 35%, with response defined by a loss of at least 5% of their body weight at the 12-month follow-up. We will also use Fisher's exact test to compare the response rates in each group, and, as a secondary analysis, will consider the use of a logistic regression to control for any other covariates of interest. To investigate possible longitudinal trends, we will fit a logistic mixed effects model, similar to the linear mixed effects model described above.

Methods: Secondary Aims

For each continuous and categorical variable at each time point, we will use a two-sample t-test and Fisher's exact test, respectively. Summary statistics (mean, standard deviation, quantiles, counts, and percentages) and plots will be produced for all demographic and study outcomes. We will investigate the effectiveness of the device by usage by including usage time as a continuous covariate in a linear model for TBWL. CTRI Biostatistics Core personnel will conduct all analyses using the latest version of R (R Foundation for Statistical Computing, Vienna, Austria. <http://www.R-project.org/>). No alpha spending function is applied to adjust for multiple comparisons across the secondary aims, and no claims will be made based on any of the secondary endpoints, which are instead viewed as hypothesis generating endpoints.

Missing Data

The primary hypotheses will be tested on the intent-to-treat population. A sensitivity analysis will be

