performed with the binary weight loss endpoint. This analysis will include a best-case scenario (assuming subjects with missing values have all lost over 5% body weight), a worst-case scenario (assuming no subjects with missing values have lost over 5% body weight), and a tipping point analysis (as described in Yan¹). We will check the assumption that the data is missing completely at random, and use multiple imputation techniques to reduce bias in the estimation of the treatment effect. Missing data will be clearly reported and included in tables.

Power Calculation

The primary outcomes are TBWL from the start of treatment until the 12-month mark and the number of subjects who lose at least 5% of their baseline total body weight. We will power both of these tests at the 0.025 significance level (a Bonferroni correction to maintain a family-wise error rate of 0.05 in our primary analysis). For TBWL, we will test the following null and alternative hypothesis:

$$\begin{aligned} H_0: \mu_t - \mu_c &\leq 5\% \\ H_1: \mu_t - \mu_c &> 5\% \end{aligned}$$

where μ_t and μ_c are the treatment and control mean TBWL in the ITT population. We will use a one-sided two-sample t-test to determine if there is a statistically significant difference in TBWL between our control and treatment arms beyond a superiority margin of 5%. With a total sample size of 90 subjects (30 sham and 60 active treatment), this t-test will have 80% power at the $\alpha = 0.025$ significance level to detect an effect size of $d = 0.63$. Assuming a similar standard deviation of TBWL as the ReShape trial (7.5%), this translates to a detectable difference in TBWL between the treatment and control groups of 4.75%. Assuming this same standard deviation, a two-sample superiority test will have 80% power assuming that the true difference between groups is 6.33%.

For the proportion of treatment subjects who lose at least 5% of their baseline total body weight, we will test the following null and alternative hypothesis:

$$\begin{aligned} H_0: P_t &\leq 35\% \\ H_1: P_t &> 35\% \end{aligned}$$

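### The responder test has 69.5% power, not the stated 80%, at one-sided 0.025, and the plan does not say which responder test or tests decide success

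*Combined protocol and SAP*

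**What the plan says.** Section 6 (Specific Aims) frames the trial as a comparison, evaluating the device "as a method of reducing excess body weight, as compared to a sham control and lifestyle modification program", and gives its regulatory purpose: "The purpose of this investigational device study is to collect data to support regulatory submissions".

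Section 9, Primary Outcome Measures, defines responder success at 12 months through the proportion of active subjects losing 5% or more of baseline weight. That proportion "is at least 35% and is approximately double the proportion in the placebo-treated group; the difference between groups is statistically significant".

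Section 9, Methods: Primary Aims, plans two responder tests. The first is one-sample: "We will use a one-sided exact binomial test to determine if the response rate in the treatment group significantly exceeds 35" per cent. The second is Fisher's "exact test to compare the response rates in each group". Only the logistic regression that follows is labelled secondary.

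Section 9, Power Calculation, sets 0.025 for each of the two primary outcomes, described as "a Bonferroni correction to maintain a family-wise error rate of 0.05 in our primary analysis". For the responder outcome it then states a null of P_t at or below 35%, 60 active subjects, 80% power at 0.025, h = 0.321 and an equivalent response rate of 50.8%. It gives no sham response rate and no hypothesis or power for Fisher's test.

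**The concern.** There are two linked problems.

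First, the stated 80% cannot be obtained from the plan's own sample size, null, alternative, sidedness and significance level. Anyone relying on it would think the responder primary better powered than it is.

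Second, the outcome definition needs a significant difference from sham, while the only responder hypothesis that is written down and powered never uses the sham arm. The plan does not say whether the one-sample test, Fisher's test or both decide success. Nor does it say whether the 35% condition is a threshold for the observed rate or the null of a test. One data set can then count as success under one subsection and failure under another, with the choice still open when the data are seen. In a trial meant for regulatory submission, that should be settled beforehand.

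**Working it through.** **Inputs.** From Power Calculation: n = 60 active and 30 sham, null rate 0.35, alternative 0.508, level 0.025. From Methods: Primary Aims: the binomial test is exact and one-sided. The sham rate is not given. I assume 25.4% (half of 50.8%, following the approximate doubling in Primary Outcome Measures) and show 20% and 30% as a range.

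**1. Reproducing the plan's figure.** The effect size is h = 2·arcsin(√p₁) − 2·arcsin(√p₀). For 0.508 against 0.35 this is 0.3207, so h and 50.8% agree. The detectable h at 80% power is (z₁₋α + 0.842)/√60:

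- one-sided 0.05: (1.645 + 0.842)/7.746 = 0.3210, the plan's figure
- one-sided 0.025: (1.960 + 0.842)/7.746 = 0.3617, a rate of 52.8%

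The stated 80% is therefore the arcsine approximation at one-sided 0.05. At one-sided 0.025 the same approximation gives 70.1% power for h = 0.321.

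**2. The exact test as specified.** P(X ≥ 28 | 60, 0.35) = 0.0412 and P(X ≥ 29 | 60, 0.35) = 0.0228, so rejection at 0.025 needs 29/60 (48.3%) or more. Power is P(X ≥ 29 | 60, 0.508) = 0.695. It reaches 80% at a true rate of about 52.9%. Even at one-sided 0.05 the exact test (28/60 or more) has 77.9% at 50.8%.

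**3. Two results that the subsections classify differently.**

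| Active | Sham | Ratio | One-sample p | Fisher p, two-sided / one-sided |
|---|---|---|---|---|
| 29/60 (48.3%) | 8/30 (26.7%) | 1.81 | 0.023 | 0.069 / 0.039 |
| 27/60 (45.0%) | 6/30 (20.0%) | 2.25 | 0.070 | 0.022 / 0.017 |

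At 0.025 the first row passes the one-sample test and fails Fisher's. The second has an observed rate above 35%, more than double sham, with Fisher's test significant, yet it fails the one-sample test.

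**4. Power under the candidate rules.** I enumerated all 61 × 31 tables at 50.8% active, with Fisher's test at 0.025 (two-sided / one-sided). An observed rate of at least 35% means 21/60 or more.

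| Assumed sham rate | Observed ≥35% plus Fisher | One-sample test plus Fisher |
|---|---|---|
| 20% | 73.6% / 77.1% | 59.2% / 61.1% |
| 25.4% | 52.0% / 56.5% | 44.8% / 48.2% |
| 30% | 34.1% / 38.6% | 30.8% / 34.7% |

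**5. How often the rules disagree.** Take 25.4% sham and compare the one-sample test alone with observed ≥35% plus Fisher, leaving the doubling condition aside. The one-sample test alone passes in 24.7% / 21.3% of trials and the other rule alone in 7.2% / 8.3%. They conflict in 31.9% / 29.6% of trials.

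**The case against.** The strongest reply is that the subsections fit together. The significance clause in Primary Outcome Measures maps onto Fisher's test and the 35% clause onto the one-sample test. Both tests sit under Primary Aims, and the 0.025 allotted to the responder outcome plausibly covers both. Leaving Fisher's test without the one-sided label used for the binomial test may imply that it is two-sided. Much of this stands: the sham comparison is planned, and its level can be inferred. What remains is that nothing says both tests must pass, the 35% clause can equally be read as an observed threshold, and Fisher's test has no assumed sham rate or power.

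A second reply is that more than 60 active subjects may be analysed, since the primary analysis is intention-to-treat with multiple imputation and 106 × 2/3 is about 70 or 71. Exact one-sample power is then 76.8% at n = 70 and 72.9% at n = 71 (the test is discrete). The gap narrows but does not close.

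A reader might also infer that a device with no effect could succeed merely because the lifestyle program lifts both arms above 35%. If the one-sample test decided alone, a shared 40% rate would pass 11.8% of the time. The documents do not support that reading, because the outcome definition requires a significant difference from sham. With both tests required at 0.025, a no-effect device passes in 0.3% to 1.5% of trials for shared rates of 35% to 60%.

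**Conclusion.** The point holds in two parts.

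The responder power is wrong as written: 69.5% rather than 80%, a shortfall of 10.5 percentage points. This rests only on the plan's own inputs. That the Bonferroni level was missed is inferred from the match between 0.321 and the one-sided 0.05 value. The shortfall does not depend on that explanation.

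The responder decision rule is unstated, and the comparison with sham that the outcome definition requires is not powered. The two example results show that this can change the conclusion in either direction. How often it would, and the power of any two-arm rule, depend on assumed sham rates.

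The documents do not show that the comparison with sham is missing, or that both tests must pass. Requiring both would raise the bar from an observed 21/60 to 29/60 and, at an assumed 25.4% sham rate, lower power from 52.0%–56.5% to 44.8%–48.2%. That choice belongs to the sponsor.

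**What to change.** 1. In Power Calculation, state the one-sample power as 69.5% at a true rate of 50.8%, or give about 52.9% as the rate detectable with 80% power, at n = 60 and one-sided 0.025.
2. In Methods: Primary Aims and Power Calculation, state one responder decision rule, fixed before unblinding. It should include Fisher's between-arm test at the endpoint's 0.025, with its sidedness, and say whether the 35% condition is an observed threshold or the one-sample test. It should also say whether the approximate doubling is a criterion (with a cut-off) or descriptive.
3. Report power for the chosen rule over a stated range of sham rates, labelled as assumptions. The table under step 4 of the working gives both candidate rules without a doubling cut-off.

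Both tests are already planned and no extra enrolment is proposed. The cost is a less favourable stated power. Choosing the two-test rule would also be a substantive decision about the success criterion. Section 8 reports 24 subjects already enrolled, so it should be documented as a dated amendment.

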where P_t is the proportion of treatment subjects who lose at least 5% of their body weight by the twelve month follow-up. With a total sample size of $n = 60$ active treatment subjects, an exact binomial test will have 80% power at the 0.025 significance level to detect an effect size of $h = 0.321$. This effect size is equivalent to observing a response rate of 50.8% in the treatment group, similar to that seen in the ReShape study. We note that our pilot data indicated that all subjects reached this endpoint, but the sample size was too small to reliably estimate an effect size for the use of powering this study (Kramer 2006).

Anticipating a drop out rate of 15%, we will plan to recruit $n = 106$ total subjects overall in the study across both sites.

Interim Analysis

No interim analysis will be performed.

Representativeness Analysis

As per the guidance from the FDA relating to the representativeness of the study population (<https://www.fda.gov/downloads/MedicalDevices/DeviceRegulationandGuidance/GuidanceDocuments/UC>

M507278.pdf?source=govdelivery&utm_medium=email&utm_source=govdelivery) the following analyses will be conducted:

For each demographic characteristic an appropriate statistical test will be conducted to flag any differences between the two respective subgroups (active and sham device). For categorical data either a Chi-square test (if $n \geq 5$ in each table cell) or Fisher's exact test (if $n < 5$ in any single table cell), will be used, and for continuous a 2-sample t-test will be used to compare the respective subgroups.

References

Yan, Lee & Li (2009). Missing Data Handling Methods in Medical Device Clinical Trials. *Journal of Biopharmaceutical Statistics*, 19: 6, 1085-1098.

Food and Drug Administration. Summary of Safety and Effectiveness Data (SSED) for ReShape Integrated Dual Baloon System. 2015.

Pre-enrollment Screening

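### The between-arm responder comparison uses Fisher's exact test with no stated sidedness or level; Boschloo's exact test would add about 4 to 9 points of power if it is one-sided at 0.025, and only about 1 to 3 points at the planning rates if it is two-sided

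*Combined protocol and SAP*

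**What the plan says.** In Section 9, Primary Outcome Measures (At 12 months), the responder outcome has three parts: an active response rate of at least 35%, a rate that "is approximately double the proportion in the placebo-treated group", and the condition that "the difference between groups is statistically significant".

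Statistical Considerations, Methods: Primary Aims, names two tests for this outcome. The first uses the active arm alone: "We will use a one-sided exact binomial test to determine if the response rate in the treatment group significantly exceeds 35" percent. The second uses the randomised sham arm: "We will also use Fisher's exact test to compare the response rates in each group". The first is called one-sided. The second has neither a sidedness nor a level.

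The Power Calculation says "We will power both of these tests at the 0.025 significance level", where the two tests are the weight-loss t-test and the single-arm binomial test. The t-test is also one-sided: "We will use a one-sided two-sample t-test to determine if there is a statistically significant difference in TBWL". The planned sizes are given there too: "With a total sample size of 90 subjects (30 sham and 60 active treatment"). The section gives no power and no sham response rate for the Fisher comparison.

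**The concern.** Fisher's test computes its p-value with the total number of responders held fixed. The design fixes the arm sizes but not that total. With 60 and 30 subjects the conditional distribution has few distinct values, so the true error rate can fall well below the nominal level.

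Boschloo's test takes Fisher's p-value as its statistic and finds the largest cut-off that keeps the error within the nominal level for every common response rate. It therefore rejects in every table where Fisher's test with the same sidedness rejects, and usually in some others.

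At stake is power for the only responder test that uses the concurrent control, and a significant result on it is part of a primary outcome. How much power depends on whether the test is one-sided or two-sided, which the plan leaves open.

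**Working it through.** **Inputs from the document.** Arm sizes are 60 and 30. The level for each powered primary test is 0.025. The active response rate comes from the Power Calculation: "This effect size is equivalent to observing a response rate of 50.8% in the treatment group". Planned recruitment is 106, from 90/(1 − 0.15) = 105.9.

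**Assumptions.** The sham rate is not given. Half of 50.8% is 25.4%, taken from the doubling criterion, and other rates are tried below. One-sided 0.025 is assumed first, because both stated primary hypotheses are one-sided at that level. Two-sided results follow.

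**The plan's own responder figure.** The only one is 80% power for the single-arm test of 35% against 50.8% with n = 60, and it concerns a different test. The exact one-sided 0.025 rule is at least 29 responders of 60: P(X ≥ 29 | 0.35) = 0.0228, whereas P(X ≥ 28 | 0.35) = 0.0412. Its power is P(X ≥ 29 | 0.508) = 69.5%, so the stated 80% is not reproduced at that level. No figure exists to reproduce for the Fisher comparison.

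**Method.** All 61 × 31 tables (x active responders, y sham responders) are enumerated.
- One-sided Fisher p(x, y) = P(H ≥ x), where H is hypergeometric: 60 drawn from 90 of whom x + y are responders.
- True size = maximum over a common rate π of Σ b(x; 60, π) b(y; 30, π), summed over the rejected tables.
- Power = Σ b(x; 60, p₁) b(y; 30, p₂) over the same tables.
- Boschloo's test rejects when the Fisher p is at or below the largest cut-off whose true size stays within the level.

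**One-sided 0.025, 60 versus 30.**
- Fisher: maximum size 0.0151. The unused share is (0.025 − 0.0151)/0.025, about 40%.
- Boschloo: the cut-off on the Fisher p is 0.0394, and the maximum size is 0.0249.
- Example: 29/60 versus 8/30 gives Fisher p = 0.0394 and Boschloo p = 0.0249.

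| Active vs sham rate | Fisher power | Boschloo power | Gain (points) |
|---|---|---|---|
| 35% vs 17.5% | 33.4% | 39.8% | 6.4 |
| 45% vs 22.5% | 47.7% | 56.7% | 9.0 |
| 50.8% vs 25.4% | 56.5% | 65.1% | 8.6 |
| 60% vs 30% | 71.5% | 76.9% | 5.4 |
| 70% vs 35% | 84.9% | 88.7% | 3.8 |
| 50.8% vs 20% | 77.1% | 83.6% | 6.5 |
| 50.8% vs 30% | 38.6% | 46.8% | 8.2 |

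**Two variations, still one-sided 0.025 at 50.8% vs 25.4%.**
- If success also needs the single-arm test (x ≥ 29), joint power goes from 48.2% to 53.6%, a gain of 5.4 points.
- If all 106 are analysed as 71 versus 35, power goes from 65.2% to 71.8%, a gain of 6.6 points. Fisher's test at 71 versus 35 thus roughly equals Boschloo's at 60 versus 30, a difference of 106 − 90 = 16 subjects.

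**Two-sided, 60 versus 30, at 50.8% vs 25.4%** (usual ordering by table probability, same ordering for Boschloo).

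| Level | Fisher max size | Boschloo max size | Fisher power | Boschloo power | Gain (points) |
|---|---|---|---|---|---|
| 0.025 | 0.0208 | 0.0250 | 52.0% | 55.1% | 3.1 |
| 0.05 | 0.0437 | 0.0492 | 61.8% | 62.5% | 0.8 |

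**The case against.** The strongest objection is that the plan does not say the Fisher comparison is one-sided. Methods: Primary Aims uses that word for the confidence intervals and for the binomial test, then omits it for Fisher's test, so a two-sided reading is at least as natural. On that reading Fisher's test leaves about 17% of the level unused at 0.025, from (0.025 − 0.0208)/0.025, and about 13% at 0.05, from (0.05 − 0.0437)/0.05. The gain is then small. With two-sided 0.05 and the binomial test also required, it vanishes: joint power is 52.1% with either test. This stands, and it is why the size can only be stated conditionally.

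A reader might infer that the plan discards 40% of its allowed error and gives up 9 points of power. The documents do not support that as a fact. Both figures need a one-sided 0.025 test, and 9 points is the top of the range even then.

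A reader might also infer that Fisher's test is wrong here. It is not: it controls the error rate and is conventional. Conditioning on the responder total also has a defence under randomisation inference, where the sharp null hypothesis fixes that total. Boschloo's test is a gain in efficiency, not a correction.

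Finally, neither test uses the stratification by gender and center, and the plan does not say how either would be combined with multiple imputation. This is true, but it does not favour Fisher's test.

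**Conclusion.** The point holds as a cheap improvement. A significant between-arm difference is part of a primary outcome, and the test named for it is valid but conservative at 60 versus 30. Its sidedness and level are not given.

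The gain from Boschloo's test is about 4 to 9 points if the comparison is one-sided at 0.025, over the rates tried at 60 versus 30. It is 5.4 points at the planning rates if the single-arm test must also succeed. At two-sided 0.025 and 0.05 it is about 3.1 and 0.8 points at those rates. All of these rest on an assumed sham rate.

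The harm is lost power, never an inflated error rate. The change does not rescue the comparison: at 50.8% versus 25.4%, even the one-sided Boschloo test has 65.1% power at 60 versus 30 and 71.8% at 71 versus 35.

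**What to change.** Before unblinding, amend Methods: Primary Aims as follows.

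1. State the sidedness and level of the 12-month between-arm responder comparison. One-sided 0.025 would match the other primary tests. This comes first because it decides how much the choice of test matters.
2. Name Boschloo's exact test for that comparison, and report Fisher's p-value as supportive.
3. Use the same test where the best-case, worst-case and tipping-point scenarios are analysed as 2×2 tables. The plan names no test for these at present.

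The cost is a change of wording. Randomisation, data collection and sample size are untouched, and the computation takes seconds in R, which the plan already uses. The one downside is a less familiar test. The change has to be written down before anyone sees outcome data by arm, because a later switch to a more powerful test would not be credible.

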- Study participants will be instructed to return home and begin using the device.
- Dietary Counseling from research dietician including review of diet and discussion of Healthwatch 360 app use – 30 minutes.

Summary of the Testing Procedures Visit 1 (0 months)

- Urine pregnancy test (if applicable – i.e. a female of child bearing potential)
- Glucose finger prick (Diabetes screening)
- Check skin behind ears (visual inspection to ensure appears healthy)
- Weight and height to calculate BMI
- Hip and waist measurements
- Fasting Insulin level

- High Sensitivity C-Reactive Protein
- Lipid Panel
- Oral Glucose Tolerance Test (OGTT)
- Pulse rate and blood pressure
- Quality of life survey (Duke University IWQOL – <http://www.qualityoflifeconsulting.com/iwqol-lite.html>)
- DXA Scan (whole body scan)
- Audiogram test including otoscope examination of the ear canals.

Summary of the Testing Procedures Visit 2 (3 months)

- Urine pregnancy test (if applicable – i.e. a female of child bearing potential)
- Weight and BMI calculation
- Check skin behind ears (visual inspection to ensure appears healthy)
- Waist and hip measurements
- Fasting Insulin level
- High Sensitivity C-Reactive Protein
- Lipid Panel
- Oral Glucose Tolerance Test (OGTT)
- Pulse rate and blood pressure
- Quality of life survey (Duke University IWQOL – <http://www.qualityoflifeconsulting.com/iwqol-lite.html>)
- DXA Scan (whole body scan)
- Coordinator asks participant to complete adverse event monitoring questionnaire.
- Audiogram test including otoscope examination of the ear canals.

Other activities at Visit 2 (3 months):

- Dietary Counseling from research dietitian including review of diet reports from Healthwatch 360 app – 15 minutes

Summary of the Testing Procedures Visit 3 (6 months)

- Urine pregnancy test (if applicable – i.e. a female of child bearing potential)
- Weight and BMI calculation
- Check skin behind ears (visual inspection to ensure appears healthy)
- Waist and hip measurements
- Fasting Insulin level
- High Sensitivity C-Reactive Protein
- Lipid Panel
- Oral Glucose Tolerance Test (OGTT)
- Pulse rate and blood pressure
- Quality of life survey (Duke University IWQOL – <http://www.qualityoflifeconsulting.com/iwqol-lite.html>)
- DXA Scan (whole body scan)
- Coordinator asks participant to complete adverse event monitoring questionnaire.
- Audiogram test including otoscope examination of the ear canals.

Other activities at Visit 3 (6 months):

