- The proportion of subjects who lose at least 5% of baseline truncal body fat in the active versus placebo treated groups. (As measured by a whole body DXA scan).
- The difference in mean percent loss of baseline visceral adipose tissue in the active versus placebo treated groups. (As measured by a whole body DXA scan).
- The proportion of subjects who lose at least 5% of baseline visceral adipose tissue in the active versus placebo treated groups. (As measured by a whole body DXA scan).

- Difference in lean muscle mass in the active versus placebo treated group. (As also automatically measured by the whole body DXA scan).
- Difference in bone mineral content in the active versus placebo treated group. (As also automatically measured by the whole body DXA scan).
- Blood pressure
- Heart rate
- Lipid profile (Assess total non-HDL cholesterol, and HDL to total cholesterol ratio)
- High-sensitivity C-reactive protein
- Oral glucose tolerance test (See Appendix 5)
- Fasting insulin level
- Waist and hip circumferences
- Body Mass Index (BMI)
- Adjustment of concomitant medication – both reduction and new medications
- Quality of life – IWQOL-Lite questionnaire. This validated instrument, developed by Duke University, has been used by a variety of researchers to assess various obesity treatment options and their impact on individual patients. The questionnaire is available in a number of languages including Spanish. A detailed description is available on this website: <https://olv.duke.edu/iwqol>. As can be seen on this website this instrument has been used extensively in studies relating to weight loss and obesity: <http://www.qualityoflifeconsulting.com/iwqol-litepublications.html>.
- Dose response analysis: it is likely that some subjects will not utilize their device for the mandated 5 hours per week. Usage data will be available from the devices as they can distinguish when they are genuinely being used as opposed to just being turned on with air between the electrodes. Data from such subjects will be analyzed in the main study but if possible a dose response analysis will also be carried out. Analysis will be in an intention to treat manner – see Statistical Considerations.

Safety Endpoints and Adverse Event Monitoring

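### Continuous secondary and safety outcomes get a plain two-sample t-test with no change score or baseline covariate stated; adjusting for each outcome's own baseline would gain precision at almost no cost

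*Combined protocol and SAP*

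**What the plan says.** Section 9, Statistical Considerations, Methods: Secondary Aims, gives one rule for all secondary outcomes: "For each continuous and categorical variable at each time point, we will use a two-sample t-test and Fisher's exact test, respectively". It does not say whether the analysed quantity is the visit value or the change since Visit 1, and it names no baseline covariate. No separate safety analysis follows that would settle this.

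The outcome definitions differ in how they treat baseline. Fat outcomes are tied to it, for example "The difference in mean percent loss of baseline total body fat in the active versus placebo treated groups". Lean mass and bone are not: "Difference in lean muscle mass in the active versus placebo treated group" and "Difference in bone mineral content in the active versus placebo treated group". Blood pressure, heart rate, lipids, C-reactive protein, glucose tolerance, insulin, waist and hip, BMI and quality of life are listed by name, with no reference to baseline.

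Section 6 frames the safety objective, relative to control, partly as "changes from baseline in vital signs (blood pressure and heart rate), and laboratory results". The Visit 1 test list in Section 9 includes every variable named above. The longitudinal weight model does use baseline, "with fixed covariates for baseline weight, time, group, and a time / group interaction", but nothing equivalent is planned for the secondary variables.

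**The concern.** Where the authors want an outcome measured against baseline, as for weight and fat, they say so. Where they do not, a t-test at each time point most naturally means a t-test on that visit's values. For blood pressure, heart rate and laboratory results, the test would then answer a different question from the one Section 6 sets.

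For lean mass, bone mineral content, waist and hip, BMI and quality of life, Section 6 makes no such promise. There the issue is efficiency. Much of the variation in a visit value was already present at Visit 1, and the unadjusted test counts it as noise. BMI shows the inconsistency well. Height is listed only at Visit 1, so percent change in BMI equals percent change in weight. The same data would be judged against baseline as a primary outcome and, on the natural reading, without it as a secondary one.

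The safety comparison has most at stake. With 30 sham participants, an imprecise test that finds no significant difference is uninformative but easily read as reassurance, in a study intended to support regulatory submissions.

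**Working it through.** **Inputs from the documents.** 60 active and 30 sham participants (Power Calculation); SD of percent weight loss 7.5% (same place). The documents give no SD, correlation or power for the secondary variables, so those used below are assumptions.

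**The plan's own figure.** The SE of a difference in means is SD × sqrt(1/60 + 1/30) = 0.2236 SD. At d = 0.63, d/SE = 0.63/0.2236 = 2.82. One-sided power at 0.025 is Φ(2.82 - 1.96) = 80.4%, or 79.6% by the noncentral t. The stated 80% is reproduced, so the same SE formula is used for the secondary variables.

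**Formulas.** With equal SD at both visits and baseline-to-follow-up correlation r:
- visit value: SE = 0.2236 SD
- change score: SE = 0.2236 SD × sqrt(2(1 - r))
- ANCOVA: SE = 0.2236 SD × sqrt(1 - r²)

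| r (assumed) | visit value / ANCOVA | visit value / change | change / ANCOVA = sqrt(2/(1 + r)) |
|---|---|---|---|
| 0.3 | 1.05 | 0.85 | 1.24 |
| 0.5 | 1.15 | 1.00 | 1.15 |
| 0.6 | 1.25 | 1.12 | 1.12 |
| 0.7 | 1.40 | 1.29 | 1.08 |
| 0.9 | 2.29 | 2.24 | 1.03 |
| 0.95 | 3.20 | 3.16 | 1.01 |
| 0.98 | 5.03 | 5.00 | 1.01 |

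Simulating 4,000 trials of 60 versus 30 at each of five correlations gave visit value / ANCOVA ratios of 1.14 (r = 0.5), 1.41 (0.7), 2.32 (0.9), 3.12 (0.95) and 5.04 (0.98), in line with the formula. A ratio of 3 needs r of about 0.94, and a ratio of 5 about 0.98.

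**Systolic pressure** (assumed SD 15 mmHg, r = 0.6 to 0.7). Visit-value SE = 15 × 0.2236 = 3.35 mmHg. ANCOVA SE = 3.35 × 0.80 = 2.68 to 3.35 × 0.714 = 2.40 mmHg. For an assumed true difference of 6 mmHg (two-sided 0.05, normal approximation), power is 43% unadjusted and 61% to 71% adjusted. Leaving baseline out is like needing 1/(1 - r²) = 1.6 to 2.0 times the sample.

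**Lean mass** (assumed SD 12 kg). Visit-value SE = 12 × 0.2236 = 2.68 kg. ANCOVA SE is 1.17 kg at r = 0.90, 0.84 kg at 0.95 and 0.53 kg at 0.98. For an assumed true difference of 2 kg, power is about 12% unadjusted and 40%, 67% or 96% adjusted.

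**BMI.** The plan's 7.5% SD of weight change gives an approximate visit value / change ratio of (between-participant coefficient of variation)/7.5%. Assumed coefficients of 12%, 15% and 20% give 1.6, 2.0 and 2.7.

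**The case against.** The strongest reply is that the plan never says visit values. Its primary analysis also applies a two-sample t-test at each time period to weight loss, which is already a difference from baseline, so that wording does not by itself imply raw values. Read with Section 6, a t-test on change is a possible reading for vital signs and laboratory results. This stands: the plan is silent, not explicit. If change was intended, ANCOVA gains less at high correlation (last column of the table) but still gains. Below r = 0.5 a change score is noisier than the visit value.

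The second reply is that the plan allows no claims from secondary endpoints. That also stands and limits the consequence. It does not remove the gain for a safety comparison that is itself a stated objective.

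Stronger readings that a reader might infer are not supported:
- **A conflict with Section 6 for every listed outcome.** The change-from-baseline objective covers vital signs and laboratory results only.
- **A standard error three to five times too large across the list.** That needs r of about 0.94 to 0.98. It is plausible for DXA lean mass and bone mineral content but is not documented, and it does not carry over to blood pressure or C-reactive protein.
- **Biased or false-positive results.** With SD 12 kg, a chance lean-mass difference of 3 kg or more has probability 0.26 (z = 3/2.68 = 1.12), but such a difference is far from significant. The unadjusted test is unbiased under randomisation and does not inflate type I error. The 0.26 also ignores stratification by gender. With an assumed within-sex SD of 8 to 10 kg, the SE is 1.79 to 2.24 kg and the probability about 9% to 18%.

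**Conclusion.** The point holds as an under-specified and inefficient analysis, not as an invalid one. The plan names only a t-test, does not define the analysed quantity and leaves collected baselines unused. For vital signs and laboratory results, the natural reading does not match Section 6. For the other outcomes the loss is precision only.

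If visit values are compared, the standard error relative to ANCOVA is larger by a factor of about 1.15 to 1.4 for measures such as blood pressure and heart rate (assumed r = 0.5 to 0.7). It is larger by about 3.2 to 5 only for DXA lean mass and bone mineral content (assumed r = 0.95 to 0.98). These factors rest on equal SDs at both visits and on correlations that the documents do not give. This is a free improvement whichever quantity the authors had in mind, and its main value is to the safety comparison.

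**What to change.** For lean mass, bone mineral content, blood pressure, heart rate, laboratory values, waist and hip, BMI and quality of life, replace the t-test with ANCOVA: the 12-month value on arm and that outcome's own Visit 1 value. Report the adjusted difference with its 95% CI. Fit the same model at months 3 and 6, or one repeated-measures model over all follow-up visits. Log-transform skewed laboratory values such as C-reactive protein and insulin at both baseline and follow-up, and report ratios of geometric means.

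The cost is a change to the analysis plan's wording, ideally made before unblinding, and about one line of R per outcome. Each model spends one degree of freedom on baseline and needs no new data. At low correlation the gain over visit values is small (1.05 at r = 0.3), but ANCOVA is essentially never less precise, unlike a change score.
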